# Qualitative study:

A thematic analysis will be undertaken identifying key emergent themes and their meaning. Transcripts will be reviewed independently by members of the research team and analysed using a constant comparative approach including searches for disconfirming evidence. This involves dividing each interview into units, identifying each discrete area through extracting significant statements

and highlighting of text in the transcripts. The units are then grouped into categories and coded based on similarities and differences. Data will be inputted into a qualitative software package NVivo and coded using this framework. After further reflection in comparing and integrating the units, they will be categorised into themes and typologies will be developed. The clusters of themes and typologies will then be referred back to the original descriptions for validation. The overall interpretation of meaning and explanations will be developed and their implications considered for the intervention development, with input from the entire research team including collaborators and PPI representatives. We will use adaptive theorising where we consider the interpretation in relation to our theoretical framework and existing theory/models of successful ageing..

### Feasibility study:

As a feasibility study, our analysis will be mainly descriptive of the recruitment, participant characteristics, baseline and outcome variables, loss to follow-up and adverse events. We will provide confidence intervals for comparisons of outcome variables between groups and estimates of their standard deviations. These will assist in choice of principal outcome variable(s) and calculating power/sample size for a full trial. We will report findings using CONSORT guidance and flowchart.

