- 6) Assess the feasibility of conducting a budget impact analysis, scaling up to Clinical Commissioning Group level, estimating where monetary costs and benefits will fall, for the NHS (e.g hospitalisation) and Local Authority (e.g personal budgets/reablement).

This plan uses the MRC model to develop a new complex intervention integrating existing evidence, relevant theories and a co-design development process involving the public and front-line health/care professionals to develop and manualise a new health promotion intervention, tailored for delivery at home to people with early frailty. We will test feasibility to recruit and randomise individuals for an RCT, and whether the intervention is acceptable and feasible to deliver in the NHS. We will determine intervention costs and potential effect sizes across a range of outcomes to inform a future RCT. We assess the feasibility of conducting a budget impact analysis to inform current debates amongst commissioners on how to provide and fund care at home and the feasibility of a cost-effectiveness analysis in the full RCT.

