Sample size, recruitment and retention: For the feasibility study we aim to recruit 50 people, 12-13 each from 4 General Practices. This number was selected as a sufficient number to test the feasibility/ acceptability of the intervention and pilot the study process, recruitment, randomisation and retention for a full RCT, and a realistic number to recruit per practice and deliver the intervention in the short time frame available for the feasibility study. Assuming an average of 600 people aged over 65 per study practice (based on our previous studies with this age group in our study settings), a prevalence of 41% of 'pre-frailty'38 would lead to a population of 246 before exclusions. Assuming (on best estimates) 30 of these are excluded, and 20% have been visited at home in the last 6 months by a health professional (including GPs, Out of Hours services, nurses, health care assistants, physiotherapist, occupational therapist or other community health professional) our eligible population would be 43 people. Assuming a conservative recruitment rate of 30% of eligible people, we could recruit 13 people per practice. In our past experience in previous studies on health promotion in the 65+ population (the WISH study) our attrition (including deaths) over 3 months was 10% and over 6 months 23%. Part of the purpose of the feasibility study is to assess if all of these assumptions are correct, as there is no data available (apart from community prevalence) that are specific to an older population with early frailty with which to base these assumptions. If our eligibility or recruitment rate is much lower than anticipated we would be able to extend our study to include further GP practices.

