# 16. Success criteria

For a feasibility study it is important to define success criteria a priori that will determine whether it is appropriate to progress to a full evaluation. For the purposes of this study in a population with early frailty we would define this as

1) A recruitment rate of a minimum of 70% of our target of 50 people within 6 months.

- 2) A retention rate of 80% at 6 months (excluding those with outcomes we are measuring as part of the study i.e. deaths).
- 3) A positive evaluation of feasibility and acceptability to older people/the NHS in the process evaluation.
- 4) On analyses of the candidate primary outcomes there is at least no difference between the two arms (ie. no negative effects).

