### 4) Recruitment

A potential concern is the identification of an eligible population with early frailty who are willing to participate in a RCT of a new intervention. We have been conservative in our estimates and have the capacity to extend to further practices if needed. Testing the recruitment process is an important output from the study.

5) Workforce capacity to deliver the intervention

This is a low risk in a small study with only 25 people receiving the intervention.

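### The plan lets between-group comparisons from about 40 completers help choose the main trial's principal outcome and sample size, which permits selection of chance highs and risks an under-powered trial

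*Protocol*

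**What the plan says.** Section 15 (Data analysis, Feasibility study) describes a largely descriptive analysis and then commits to two products: "We will provide confidence intervals for comparisons of outcome variables between groups and estimates of their standard deviations". The next sentence gives their use: "These will assist in choice of principal outcome variable(s) and calculating power/sample size for a full trial". Its opening pronoun refers to both products, the comparisons as well as the SDs.

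Section 7 (Aims and objectives), in the paragraph after the numbered objectives, says: "We will determine intervention costs and potential effect sizes across a range of outcomes to inform a future RCT". An effect size is a between-group quantity, so this section too gives the comparisons a role in planning.

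On size, Section 13 (Sampling, Feasibility study) says "For the feasibility study we aim to recruit 50 people, 12-13 each from 4 General Practices". Its reason concerns feasibility, not the precision of any outcome: "This number was selected as a sufficient number to test the feasibility/ acceptability of the intervention and pilot the study process". Section 17 implies equal arms: "This is a low risk in a small study with only 25 people receiving the intervention".

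No section names a minimum important difference or any other outside basis for the main trial's target difference.

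**The concern.** A small feasibility study can give a usable SD and usable recruitment and retention rates. It cannot give a usable treatment effect. If the observed differences help decide which outcome becomes principal, outcomes that happened to look good are favoured. If the same differences then feed the sample size, the inflated effect carries over and the main trial comes out too small. Both steps use the same data, so the errors compound.

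This is not a detail left open for a statistical analysis plan. The protocol itself states the use of the comparisons, and informing a full trial is one of the study's listed outputs (Section 24). The feasibility study's own conclusions on recruitment, retention and acceptability are not affected.

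**Working it through.** **1. The plan's own figures.** Section 13 gives 600 people per practice and 41% pre-frail: 600 × 0.41 = 246. Then (246 − 30) × 0.20 = 43.2 eligible, and 43.2 × 0.30 = 12.96, the stated 13 per practice. Four practices at 12.5 give 50. The figures reproduce. The protocol states no power, SD or effect size for any outcome.

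**2. Completers at 6 months.** Section 13 reports from an earlier study that "our attrition (including deaths) over 3 months was 10% and over 6 months 23" per cent, so 50 × 0.77 = 38.5. Section 16 requires "A retention rate of 80% at 6 months", not counting deaths, so 50 × 0.80 = 40. I use 20 per arm.

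**3. Precision of one comparison, in SD units.** SE = √(2/20) = 0.316. The 95% half-width is t(0.975; 38 df) × SE = 2.024 × 0.316 = 0.64. With 38.5 completers it is 0.65. Power at 20 per arm (two-sided 5%) is 9%, 16% and 35% for true effects of 0.2, 0.3 and 0.5 SD.

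**4. Precision of the SD.** With 38 df, the 95% confidence limits are 0.82 and 1.29 times the observed SD (−18% to +29%). That is imprecise but usable.

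**5. Number of candidate outcomes.** Section 14 lists about 17. By my count 12 are scores or continuous measures: EQ-5D, Barthel, Frailty Index, gait speed, grip strength, well-being, GHQ-12, BMI, IPAQ, AUDIT-C, MoCA and ICECAP-O.

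**6. Largest of 12 differences when nothing works.** By simulation (100,000 runs, SE 0.316), it averages 0.52 SD if the outcomes are independent and 0.37 SD if their correlation is 0.5.

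**7. What sizing on such a difference would cost.** Assumptions, none from the documents: the same true effect of 0.3 SD on every outcome, correlation 0 to 0.5, main trial at nominal 90% power and two-sided 5%. The formula is n per arm = 2 × ((1.960 + 1.282)/d)². At the true d = 0.3 this gives 234 per arm.

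| Route to the sample size | Median n per arm | Median true power | Mean true power |
|---|---|---|---|
| Largest of 12 observed effects, correlation 0 | 33 | 23% | 25% |
| Largest of 12 observed effects, correlation 0.5 | 48 | 31% | 39% |
| Largest of 6, correlation 0 | 45 | 30% | 34% |
| Largest of 6, correlation 0.5 | 60 | 38% | 46% |
| One pre-chosen outcome, its own observed effect* | 128 | 67% | 65% |
| Fixed target of 0.3 SD, only the SD from this study | – | 90% | 88% |

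*Among the 74% of runs in which the observed effect exceeded 0.1 SD.

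Check of the first row: with n = 33, 0.3/√(2/33) − 1.960 = 1.219 − 1.960 = −0.741, and Φ(−0.741) = 0.23. In the first two rows the mean selected effect is 0.82 and 0.67 SD, against a true 0.3. In the last row the 5th to 95th percentile of true power is 75% to 97%.

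**The case against.** The strongest reply is that the plan does none of this. The comparisons and SDs are only to assist. No rule selects the outcome with the largest difference, and none makes an observed difference the target. The SDs are a standard input to a sample size, and the last row of the table shows they serve well. Confidence intervals are reported rather than tests, so the imprecision will be visible. Objective 4 in Section 7 also tests the suitability of the outcome measures, and Section 5 lists the acceptability of assessments, so outcome choice has other grounds. The one explicit decision rule on between-arm results, criterion 4 in Section 16, checks for negative effects and does not look for the most favourable outcome.

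All of that stands, and it limits the point. A reader might infer that the protocol commits to picking the best of 12 outcomes and sizing on it, or that the main trial will certainly be under-powered. The text supports neither. A reader might also take the design of the main trial to be this study's main purpose. It is one output among several: the aim in Section 7 is to develop the intervention and test its feasibility and acceptability, and Section 18 plans a main trial only if applicable.

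What the reply does not remove is the stated use. The comparisons are named among the inputs, Section 7 repeats the role for effect sizes, and nothing keeps the observed difference out of either decision.

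**Conclusion.** The point holds as a matter of wording that permits a poor method. Between-group comparisons with a 95% confidence interval of about ±0.64 SD are given a part in choosing the principal outcome and in sizing the full trial, and they are too imprecise for either. The completer numbers and the interval follow from the protocol's figures, taking equal arms.

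The power figures show what misuse would cost, not what this plan will produce. They rest on 6 or 12 outcomes, a common true effect of 0.3 SD, correlations from 0 to 0.5, and sizing on the largest observed effect. Even without selection, sizing one pre-chosen outcome on its own observed effect gives a median power of 67% in place of 90%.

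A reader might also fault Section 15 for not saying whether comparisons are adjusted for baseline values. That is detail a statistical analysis plan commonly holds, and it forms no part of this point.

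**What to change.** Replace the sentence on use in Section 15 with wording such as:

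*The principal outcome for a full trial will be chosen on completeness, acceptability, floor and ceiling effects, variability, and relevance to older people and stakeholders, and not on the size of the observed between-group difference. The target difference will be a justified minimum important difference from outside this study. This study will supply the standard deviation, with allowance for its imprecision, and the attrition and recruitment rates.*

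Keep the between-group confidence intervals as descriptive results. Reword the mention of potential effect sizes in Section 7 to match.

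One way to allow for imprecision is the one-sided upper 80% confidence limit of the SD. At 38 df it is 1.116 times the observed SD, and since 1.116² = 1.245 it raises the sample size by about a quarter. The choice of limit is a matter of judgement.

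The cost is two changes of wording and no new data. The downside is that the planned main trial may look larger than one based on an observed effect.

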# **Health Economic Analysis:**

We will assess the feasibility of conducting a cost-effectiveness analysis of the intervention compared to treatment as usual alongside a full RCT. We will calculate the mean incremental cost per quality adjusted life year gained (QALY) for the duration of the trial and report this from the cost perspective of the NHS and personal and social services (PSS). A secondary analysis will also report the incremental cost per QALY gained from a societal perspective to capture the impact on carers and any patient out of pocket costs for health and social care. Health and social care resource use, out of pocket expenses and carer impact will be collected in the intervention and control group for the duration of the trial using a modified version of the client services receipt inventory (CSRI). We will assess the feasibility of collecting some health care resource use, primarily primary and secondary care NHS contacts, from patient records. Resource use will be costed using published national reference costs and data published by the Personal Social Services Research Unit. The cost per patient of the intervention including staff salaries and oncosts, travel costs,

consumables, estates and training will be calculated. QALYs will be calculated from the EQ-5D and the UK algorithm for calculating utility scores. We will calculate the area under the curve of the intervention versus the control group for the 6 month duration of the trial, adjusting for baseline differences in utility score. Confidence intervals will be constructed using non-parametric bootstrapping and a cost-effectiveness acceptability curve will be reported. One and two way deterministic sensitivity analyses will also be conducted for any key assumptions made. Given the importance of this issue to commissioners, we will assess the feasibility of conducting a budget impact analysis for the NHS and Local Government to reflect the cost of the intervention for their population alongside any cost savings that could be realised for that organisation.

### **Process Evaluation:**

We will conduct a descriptive analysis of quantitative questionnaire data on the acceptability/satisfaction with the intervention components, and a thematic analysis of the open questions on the questionnaires and interview data using the process described above in the qualitative study analysis section.

# 16. Success criteria

For a feasibility study it is important to define success criteria a priori that will determine whether it is appropriate to progress to a full evaluation. For the purposes of this study in a population with early frailty we would define this as

1) A recruitment rate of a minimum of 70% of our target of 50 people within 6 months.

- 2) A retention rate of 80% at 6 months (excluding those with outcomes we are measuring as part of the study i.e. deaths).
- 3) A positive evaluation of feasibility and acceptability to older people/the NHS in the process evaluation.
- 4) On analyses of the candidate primary outcomes there is at least no difference between the two arms (ie. no negative effects).

# 17. Barriers/risks

We will create and monitor a risk register throughout the study. We have identified the following potential risks:

1) Lack of evidence specific to population.

We will address this by including studies where those with early frailty have been included as a sub-population, e.g. RCTs of home-based interventions with a broader older population. If the range of

relevant behavioural techniques used is limited, we will also draw on evidence/theory from other relevant populations/settings.

# 2) Poorly developed intervention

We have put in considerable efforts to engage with a wide range of stakeholders/older people to develop the intervention, which would be based on a sound theory/evidence base. We will ensure a good representation of sectors and diverse populations in the development process.

3) Lack of local engagement We have had considerable enthusiasm from CCGs/clinicians we have consulted with in the development of this protocol. There is a widespread recognition of the importance of this work. The workload for practices/community health services is small, as patient identification centres only. We have good working relationships with our Primary Care Research networks and NoCLoR to help recruit practices if needed.

### 4) Recruitment

A potential concern is the identification of an eligible population with early frailty who are willing to participate in a RCT of a new intervention. We have been conservative in our estimates and have the capacity to extend to further practices if needed. Testing the recruitment process is an important output from the study.

5) Workforce capacity to deliver the intervention

This is a low risk in a small study with only 25 people receiving the intervention.

# 6) Harms from intervention

There are low risks of harm e.g. falls in people becoming more active, or increased carer burden in supporting the participant to make changes. We will highlight these in seeking informed consent and develop a system to identify and act on these if they occur.

# 7) Attrition/serious adverse events

With this population we would expect a higher rate of hospitalisation, inter-current illness, moves into residential care and mortality, impacting on attrition. We will report adverse events, monitor for capacity to consent with deteriorating health, and continue to follow-up where possible if the participant moves.

### 8) Delivering on time

This will be a tightly run study to keep to schedule with multiple components in 30months. We are an experienced, dedicated team that has delivered on other similar studies in short time frames. We have set a later start date (Sept 2014) in order to have all NRES, local governance, NIHR Clinical Research Network portfolio, Service Support Costs approvals in place before we start. We

are already engaged with our study sites, and have had interest in participation from several GP practices.

# 18. Plan of investigation and timetable

The project plan and key milestones are indicated in the project timetable below.

| Month               | Task  |
|---------------------|---|
| Sept – Nov 2014     | Evidence searching/extraction systematic reviews Engage stakeholders, finalise study site recruitment Focus groups, in-depth interviews.  |
| Dec - Feb
2015   | Evidence review, quality assessments, coding, synthesis Complete in-depth interviews, focus groups, start qualitative analysis. Set up intervention development panels Interim Reporting  |
| Mar - May
2015   | Complete qualitative analysis Complete systematic reviews synthesis data Co-design development panels (May 2015) Draft papers systematic reviews/qualitative work   |
| Jun - Aug
2015   | Ethics substantial amendment feasibility study Recruit research nurse Manualise intervention  |
|                     | Develop training programme Set up study sites feasibility study Set up database CRFs, randomisation service (via PRIMENT) Interim Reporting   |
| Sept – Nov
2015  | Complete feasibility study set up (Sept 2015) Training for people delivering intervention (Sept 2015) Begin recruit participants feasibility study (from Oct 2015) Baseline assessments Deliver intervention. Dissemination systematic reviews/qualitative work |
| Dec 2015 – Feb 2016 | Continued recruitment participants feasibility study Deliver intervention 3 month follow-up assessments Interim Reporting   |
| Mar – May 2016      | Complete recruitment participants (by end Mar 2015) 3 & 6 month follow-up assessments Start process evaluation.   |
| Jun – Aug 2016      | Complete 3 month follow-up assessments (Jun 2015) 6 month follow-up assessments Process evaluation Interim reporting  |

| Sept-Nov 2016  | Complete 6 month follow-up (by end Sept 2015) |
|----------------|---|
|                | Complete process evaluation                   |
|                | Feasibility study analysis                    |
|                | Economic analysis                             |
|                | Draft papers                                  |
| Dec – Feb 2017 | Refine manual                                 |
|                | Final report                                  |
|                | Dissemination                                 |
|                | Plan main RCT (if applicable).                |

# 20. Approval by ethics committees

There are ethical issues as this project is with vulnerable older people, and we will seek NRES approval for the qualitative study, intervention development and feasibility study. Ethical issues will include assessing capacity to consent and ensuring fully informed consent, in particular for those with some impaired cognition or where English is a second language. We will provide translators and translated study materials where appropriate, and act in accordance with the Mental Capacity Act 2005 and Good Clinical Practice (GCP) guidance. There may be some small risks associated with the intervention, for example falls in someone who is increasing their activity levels as a result of the intervention, and these will be fully explained to participants prior to consent. We will

set up and maintain a risk register, and report any adverse events which may occur according to GCP guidance. If the researchers identify any participants where there are concerns about their welfare, such as adult safeguarding concerns, then this will be discussed with the CI (who is a practicing GP) and the appropriate services to support them would be informed (e.g. GP or adult services), with their consent unless there is very high level risk. We will request permission from participants for longer term follow-up using routinely collected data (e.g. their GP medical records, Hospital Episode Statistics and mortality).

The first year of the study will be busy in undertaking the systematic reviews and the qualitative study, and these and the intervention development work would need to be completed before final ethical approval is sought for the feasibility study. To avoid excessive delays in the progression from the intervention development to the feasibility study, we would seek ethical approval for the overall study prior to the start date of the grant, and submit a substantial amendment with the final version of the intervention before the feasibility study.

